## **2.1 Aim 1 – Examining the Impact of Passive Provider Feedback vs. Active Provider Feedback**

### **2.1.2 Primary Implementation Science Trial Outcome – % of Prescriptions that Represent Potentially Inappropriate Medications (PIMs)**

The primary aim of the study is to compare the effectiveness of the EQUIPPED intervention to reduce the proportion of PIM prescriptions using active vs. passive processes for provider feedback aimed at improving prescribing toward older Veterans in the ED setting. PIMs will be defined according to the Beers criteria, which list medications that should generally be avoided in older adults. The Beers criteria have been used extensively in PIM research in the outpatient setting, along with data supporting the use of PIM measurement as an overall measure for better prescribing quality. Data on PIMs and all prescriptions will be gathered from the CDW from the eight VAMCs 6 months before and 12 months after the intervention period. As detailed in the power calculation, the study requires a minimum of 100 prescriptions per month

for older Veterans at each site. It is likely that most EDs will have many more than the required 100 prescriptions per month during the sampling period. The limit is above 100 because it is likely some EDs will have lower overall patient volumes, especially for older Veterans. Using our previously developed code (SQL) for the current EQUIPPED QI sites, we will be able to collect data needed to determine monthly PIM rates, number of older Veterans ( $\geq 65$  years of age) seen monthly, number of older Veterans who were discharged home, number of prescriptions for these discharged Veterans, and the number of PIMs, including specific drugs. For the sites, we will be able to describe the volume of ED visits overall and for older Veterans, the number of providers, and the number of overall prescriptions. We will ensure data validity by checking for inter-rater agreement on 10% of the data gathered by CDW and chart review at each site by the champions. **The primary endpoint will be the reduction in PIM risk from baseline to 12-months after the EQUIPPED Intervention, with a benchmark goal of <5% at each site.** We have data suggesting that PIM risks vary at sites from 7.4-11.8% at baseline (standard deviation of 0.8 to 1.9).

We are applying for waivers of informed consent and HIPAA authorization to allow for collecting prescription and related health data originating in the VA electronic health record for qualifying patients seen in randomized Emergency Departments.

### 2.1.3 Aim 1 Data Analysis Plan

The statistical analysis plan described below may be adjusted based on changes in statistical science methods and/or to fit the specific mathematical properties of collected data.

The primary efficacy outcome of interest is the % of prescriptions that are PIMS as defined according to the Beers criteria prescribed to adults aged 65 and older and discharged from the ED. Poisson regression will be used to evaluate the number of PIMs prescribed for 6 months prior to the first EQUIPPED intervention at each site compared to at least 12 months of prescribing data following the implementation of EQUIPPED provider feedback at the local site. The total number of prescriptions will be used as an offset term to account for differing volumes of prescriptions between sites as well as potentially over time. We will not have a single date of implementation as the implementation period will begin based on local scheduling. The implementation timeline will vary by site. Poisson regression will be used to evaluate the effect of the two methods of provider feedback on prescribing behavior of PIMs by including randomization group as a variable in the model. If the Poisson model demonstrates over (or under) dispersion other, related, models will be explored, e.g., negative binomial. Analyses will be conducted using SAS version 9.4 (SAS Institute, Cary, NC). Our primary aim, on which we will base sample size, is the evaluation of the EQUIPPED implementation. We will have 6 months of pre- and 12 months of post data including hospital site, provider ID, total prescriptions, and PIMs.

We will conduct three analyses for the primary outcome of monthly PIM prescribing to assess the impact of both the initially recruited, randomized sites and the newly recruited VA facility's inclusion. The analyses will be conducted as follows:

- 1) Intention to treat analysis: Include eight originally randomized sites

- 2) Per protocol analysis: Include seven originally randomized sites that implemented EQUIPPED
- 3) Per protocol analysis: Include seven originally randomized sites that implemented EQUIPPED + the non-randomized 8th site that was added to the Active Provider feedback EQUIPPED group

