**Research Methods**

**2.0 Design**

In a parallel cluster randomized trial, we will randomize 8 VA facilities to implement the EQUIPPED QI intervention with either passive provider feedback (4 sites) or active provider feedback (4 sites). Specifically, it is anticipated that all sites will implement EQUIPPED components including: didactic education concerning the Beers Criteria; decision support by order sets; and monthly provider prescribing feedback. However, *passive* provider feedback sites will implement monthly provider feedback via an electronic dashboard with audit, feedback and peer benchmarking, while *active* provider feedback sites will implement one-to-one (1:1) in-person academic detailing from a professional colleague that includes in-person audit, feedback, and peer benchmarking and provide on-site expertise. To compare the effectiveness of EQUIPPED with in-person academic detailing including proactive feedback (*active feedback*) versus EQUIPPED with passive electronic audit and feedback (*passive feedback*) intervention, we will evaluate the monthly proportion of PIM prescribing as % of individual prescriptions (primary outcome) in each arm. It is hypothesized that the decline in PIM rates will be greater in the presence of EQUIPPED with active feedback compared to EQUIPPED with passive feedback.

After the initial recruitment and randomization, one of the eight sites had to pause order set development due to COVID-19 and an off-site detail of one of the core implementation team members. After several months of stalled progress with EQUIPPED implementation, the site decided to pause EQUIPPED implementation until at least spring 2021. We have recruited an additional site to fill the open study spot. We will continue to collect prescribing data from both sites and collect implementation evaluation data from the newly recruited facility based on the timeline for the award. If the initial facility determines they can move forward in 2021, we propose collecting implementation evaluation data as originally planned (would increase number of sites to n=9). The data analysis plan for this change is reflected below in section 2. 1. 3.

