Aim 2: The formative analysis could be impacted by two types of dropouts: individual (provider) dropout and cluster (facility) dropout. Individual dropout could occur if providers fail to complete follow-up surveys. If this occurs, we will use the data we have collected to that point. All surveys will occur via email and will be brief (20 minutes or less). Providers will receive up to 5 email reminders to complete surveys. Facility dropouts could occur for various reasons, e.g. if the respective facility is not ready to implement EQUIPPED or leadership refuses to participate. We will minimize dropouts by working closely with the facility EQUIPPED champion to define the needed resources prior to the site's commitment to participate. During the implementation period, the team at the Atlanta site of the Birmingham/Atlanta GRECC will conduct bi-weekly conference calls for the site champions to discuss the team's local implementation strategy and identify strategies to address challenges. Separate calls will be held for sites randomized to passive feedback versus active feedback EQUIPPED to prevent influencing the provider feedback process at passive feedback sites. During calls, the site champions will have time to review cases, ask questions, and receive advice from the implementation team and other site leads. The EQUIPPED team has experience conducting similar calls nationally for the current VA sites since 2013.

Aim 3: The analysis will be based on data from available time logs from each facility. Our team has extensive experience using time logs with clinicians. While we will seek to collect time logs from each facility, the time for collected thought the logs will be averaged across logs/facilities, reducing the impact of any missing data from time logs. Other information is based on generally available national information on salaries by position type (not any information from individual people).

6. Definitions of covariates to be included in adjustment models

Aim 1: We will include stratum (high vs. low prescriber of PIMs at the facility level) and randomization group (active vs. passive feedback).

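### Unequal pre and post windows around site-specific start dates, with no season or calendar-time term, bias each pre-post change, and bias the arm contrast whenever timing differs by arm

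*Protocol*

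**What the plan says.** Protocol 2.1.3 and SAP section 1 give the same Aim 1 regression. The baseline is "the number of PIMs prescribed for 6 months prior to the first EQUIPPED intervention at each site"; the comparison period is "at least 12 months of prescribing data following the implementation of EQUIPPED provider feedback at the local site". The windows have different anchors: one ends at the first EQUIPPED activity, the other begins with provider feedback. Later in the same paragraph the Protocol says "We will have 6 months of pre- and 12 months of post data including hospital site, provider ID, total prescriptions, and PIMs", so the post window is stated both as open-ended and as 12 months.

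On timing, the plan says "We will not have a single date of implementation as the implementation period will begin based on local scheduling" and "The implementation timeline will vary by site". No site's start date is given.

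On model terms, section 2.1.3 names the pre/post comparison, randomization group and an offset for total prescriptions. SAP section 6 adds, for Aim 1: "We will include stratum (high vs. low prescriber of PIMs at the facility level) and randomization group (active vs. passive feedback". Neither document names a season, calendar-month, trend or COVID-19 term, and neither writes an arm-by-period term.

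Protocol 2.0 records that "one of the eight sites had to pause order set development due to COVID-19". That site then paused until at least spring 2021 and another was recruited. The analytic response in 2.1.3 is three site sets, with the regression unchanged. The third set adds the non-randomized site to the active arm.

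**The concern.** A 12-month post window averages over a full seasonal cycle and a 6-month baseline does not. Each site's change therefore carries a seasonal component that depends on its start month. A shift in the PIM percentage during the study enters the change according to how much of each window it covers. The offset corrects for prescription volume, not for a change in the percentage itself.

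This matters first for the primary endpoint as worded in Protocol 2.1.2, the reduction from baseline to 12 months, which is distorted whatever the balance between arms. It matters second for the arm comparison. A shift common to both arms cancels only if start dates, the gap between the two anchors, and post-window lengths match by arm. These are settled locally, the stratified randomization in SAP section 3 does not address them, and four sites per arm make chance imbalance likely.

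**Working it through.** **Inputs from the documents.** 4 v 4 sites; 6 pre and 12 post months; at least 100 prescriptions per site-month; 7.1% baseline PIM rate (Protocol 2.0, 2.1.2-2.1.4); 40% reduction (SAP Table 2); annual volumes (SAP Table 1). **Assumed, because the documents give none:** seasonal amplitude, step size, trend, spread of start dates, a two-sided 5% test, and an arm-by-period term as the arm effect.

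**1. The plan's own figure.** 8 × 100 × 6 = 4,800 and 8 × 100 × 12 = 9,600. For 7.1% v 2.1%: z = 0.05 / √(0.071 × 0.929/4,800 + 0.021 × 0.979/9,600) = 0.05/0.00399 = 12.5. Power exceeds 99.99%, so the stated figure reproduces. It concerns a pre-post change counted in prescriptions and does not bear on calendar time.

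**2. Quantity examined.** Each site's spurious log change is the mean calendar effect over its post months minus that over its pre months. D is the active mean of these minus the passive mean. With matching starts and windows D = 0, so the ratio of rate ratios is 1.000 for any season, step or trend.

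**3. Season**, A·sin(2πm/12).
- The 12-month mean is 0. The largest 6-month mean is A(0 + 0.5 + 0.866 + 1 + 0.866 + 0.5)/6 = 0.622A, so the largest single-site bias is 3.1%, 6.2% or 9.3% for A = 5%, 10% or 15%.
- With random start months the SD of the 6-month mean is 0.644A/√2 = 0.455A. The SD of D is 0.455A × √(1/4 + 1/4) = 0.322A, or 1.6%, 3.2% or 4.8%.
- If the arms start in opposite half-years, A = 0.10 gives exp(-2 × 0.622 × 0.10) = 0.88. If one site of four does, 0.97.
- With 12 pre-months these terms are zero.

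**4. Common step of log size 0.20.** A site starting s months after the step carries a fraction 1 + s/12 of it for s from -6 to 0, and 1 - s/6 for s from 0 to 6.
- Over s = -6 to 6 the SD of this fraction is 0.283, so the SD of D is 0.20 × 0.283 × √0.5 = 4.0%.
- With starts within 3 months either side, the fraction's SD is 0.153 and D's is 2.2%.
- With 12 pre-months and starts within 6 months, the second branch becomes 1 - s/12 and the SD of D is still 2.2%.
- Steps of 5% or 10% scale the 4.0% to 1.0% or 2.0%.
- If the step falls at the passive start and active sites start 6 months later, the false ratio is exp(-0.20) = 0.82. If one active site of four starts late, it is about 0.95, the pattern closest to the third site set.

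**5. Log-linear trend.** With equal windows it cancels, even with starts 9 months apart. At -0.10 to -0.20 per year, 18 v 12 post months moves the post midpoint by 3 months: exp(-0.10 × 3/12) = 0.98 to exp(-0.20 × 3/12) = 0.95. An implementation gap of 6 v 1 months gives exp(-0.10 × 5/12) = 0.96 to exp(-0.20 × 5/12) = 0.92.

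**6. Scale.**
- At 100 per site-month, each arm expects 2,400 × 0.071 = 170.4 PIMs before and 4,800 × 0.0426 = 204.5 after. The SE of the log contrast is √[2(1/170.4 + 1/204.5)] = 0.147. At 600 it is 0.147/√6 = 0.060.
- SAP Table 1 implies 7,164/12 = 597, 7,756/12 = 646 and 18,868/12 = 1,572 per month at the first three recruited sites.
- Adding an SD of 0.040: at 600, √(0.060² + 0.040²) = 0.072, so a nominal 5% test rejects about 10% of the time. At 100, √(0.147² + 0.040²) = 0.152, about 6%.
- Poisson simulation agrees (600 datasets per scenario, null arm contrast, starts random over 19 months, assumed season and step). At 600 per month, false positives are 9-12%, or 10-15% if active sites start 6 months later, falling to about 4-6% with season, trend and step terms. At 100 per month they are 5-8% without the terms and 4-8% with them (simulation error about 1 point).

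**7. Calendar terms need site effects.** Take noise-free counts with no season, no step, no arm effect, site baselines spread over 7.4-11.8% (Protocol 2.1.2) and starts random over 13 months. The arm-by-period model without calendar terms has error 0. Adding calendar-month effects alone gives an error SD of about 2.1%, because the months absorb which sites contribute when. Adding site effects returns it to 0.

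**The case against.** A parallel design already removes shifts common to both arms when timing is balanced, and removes a log-linear trend even when starts differ, if windows are equal. That stands, and it makes the effect on the arm contrast conditional. A reader might infer that season and secular shifts necessarily enter the contrast, or that start dates are known to be unbalanced. The documents support neither, since they give no dates. With random starts the error averages zero across hypothetical trials: it is extra variance, not a bias of known sign.

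A reader might also infer that all sites' windows straddle the pandemic. The documents show one stalled site, attributed partly to a staff detail, and one replacement. They do not show that the PIM percentage shifted.

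The post window is elsewhere given as 12 months or one year (Protocol 1.5.1 Stage 3 and 2.1.2; SAP section 2), so the open-ended phrase may be loose wording. The magnitudes rest on assumed amplitudes, and at the planning minimum time terms bring no clear gain. All of this stands.

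The clause in Protocol 2.1.3 allowing the analysis to be adjusted is a weaker answer. It names no time term, and choosing one after seeing the data is the discretion that a prespecified plan should remove.

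**Conclusion.** The point holds in conditional form. The planned comparison leaves season and period shifts in each site's and each arm's pre-post change. They bias the active-passive contrast when start dates, implementation gaps or post lengths differ by arm, which the plan does nothing to prevent. Exposure is most concrete in the third site set, where a later-recruited, non-randomized site joins the active arm. In the intention-to-treat set, the paused site has no start date while it remains paused, so its windows are undefined.

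The size cannot be learned from the documents. Under the stated assumptions the chance error in the contrast has an SD of 1.6-4.8% from season and about 2-4% from a 20% step. That is minor beside an SE of 0.15 at 100 prescriptions per site-month and material beside 0.06 at about 600, roughly the volume of two of the three sites in SAP Table 1. Variation between sites in their true response was not simulated. The change is worth making before analysis; the documents do not show that the arm comparison is already biased.

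**What to change.** - Analyse site-month counts with the log(prescriptions) offset, site effects, a pre/post term and calendar-time terms: either annual harmonics plus a COVID-19 period indicator with dates fixed in advance, or an effect for each calendar month. Take the arm effect from arm-by-period. The site effects are essential (step 7).
- Extend the retrospective CDW baseline pull to 12 months. This removes stable seasonality but not a COVID-19 shift, which still needs its own term.
- Use exactly 12 post months at every site and reconcile the two statements of the post window.
- Define the paused site's pre and post windows for the intention-to-treat set.
- Report each site's first-intervention and first-feedback dates by arm.

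The cost is a few model degrees of freedom, somewhat older baseline data, one longer run of an existing query, and amended wording in both documents wherever 6 baseline months are specified (including Protocol 1.5.1 and 3.2).

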Aim 1 Data Analysis Plan: The primary efficacy outcome of interest is the % of prescriptions that are PIMS as defined according to the Beers criteria prescribed to adults aged 65 and older and discharged from the ED. Poisson regression will be used to evaluate the number of PIMs prescribed for 6 months prior to the first EQUIPPED intervention at each site compared to at least 12 months of prescribing data following the implementation of EQUIPPED provider feedback at the local site. The total number of prescriptions will be used as an offset term to account for differing volumes of prescriptions between sites (Table 1) as well as potentially over time. We will not have a single date of implementation as the implementation period will begin based on local scheduling. The implementation timeline will vary by site. Poisson regression will be used to evaluate the effect of the two methods of provider feedback on prescribing behavior of PIMs by including randomization group as a variable in the model. If the Poisson model demonstrates over (or under) dispersion other, related, models will be explored, e.g., negative binomial. Analyses will be conducted using SAS version 9.4 (SAS Institute, Cary, NC). Our primary aim, on which we will base sample size, is the evaluation of the EQUIPPED implementation. We will have 6 months of pre- and 12-months of post data including hospital site, provider ID, total prescriptions, and PIMs.

Sample Size and Power Considerations

Power estimates are based on **Aim 1**, hypothesis 1 (i.e., primary outcome of change). The primary outcome is at the level of the individual prescribing decision. We plan to engage a total of eight VA sites with at least 1,200 eligible prescriptions per year to patients ages 65+ per ED. This will provide a total of approximately 4,800 eligible prescriptions during the pre-implementation period and 9,600 eligible prescriptions during the post time period. It can be reasonably assumed that these eligible prescriptions will be equally distributed between the randomization groups. Based upon the data presented in table 1, we estimate that approximately 7.1% of these total prescriptions at baseline will be Beers PIMS. Given this sample size, we have near 100% power to detect an absolute change in the risk of PIMs of 5% (i.e., 7.1% to 2.1%).

Table 1. Characteristics of First Three Recruited Sites (FY16 data)

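### The Aim 1 hypothesis is a greater decline from baseline, but the only stated arm comparison is a group term in a model of pre and post data; the change contrast is not written

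*Protocol*

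**What the plan says.** The hypothesis in Protocol 2.0, repeated under Specific Aim 1 in the SAP, is that "the decline in PIM rates will be greater in the presence of EQUIPPED with active feedback compared to EQUIPPED with passive feedback". Protocol 2.1.2 and SAP section 2 define the endpoint in the same terms: "The primary endpoint will be the reduction in PIM risk from baseline to 12-months after the EQUIPPED Intervention".

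The analysis is in Protocol 2.1.3 and, in nearly the same words, SAP section 1. PIM counts from 6 months before and at least 12 months after implementation go into a Poisson regression, with total prescriptions as offset. The effect of the feedback method is assessed "by including randomization group as a variable in the model"; the SAP likewise refers to "prescribing behavior of PIMs by including randomization group as a variable in the model". SAP section 6 lists two Aim 1 variables, stratum and randomization group. Neither document names a group-by-period term, a difference in change, a baseline-adjusted post comparison or a baseline PIM covariate.

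Protocol 2.1.3 adds that the plan "may be adjusted based on changes in statistical science methods and/or to fit the specific mathematical properties of collected data", and that related models such as the negative binomial will be explored if the Poisson model shows over- or under-dispersion.

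**The concern.** A group term fitted to stacked pre and post data does not estimate a difference in decline. It compares the arms' average PIM rates over both periods, and one third of the planned prescriptions (4,800 of 14,400) predate implementation. A period main effect removes the overall time change but leaves the group coefficient where it was. Only an interaction, or a post-period comparison adjusted for baseline, answers the stated question.

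Two things are at stake. An analyst who follows the sentence as written gets an effect that is diluted, or contaminated by baseline differences between two groups of four sites. An analyst who follows the hypothesis instead must choose the contrast, and the documents do not say which one. The scale is open too: SAP section 1 claims "near 100% power to detect an absolute change in the risk of PIMs of 5" percentage points (7.1% to 2.1%), an absolute change, while the Poisson model yields ratios.

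**Working it through.** **The plan's own figure.** Protocol 2.1.4 and SAP section 1 give near 100% power for 7.1% to 2.1%. Assume two-sided alpha 0.05 (none is stated) and independent prescriptions. For 4,800 pre against 9,600 post, SE = √(0.071×0.929/4,800 + 0.021×0.979/9,600) = 0.0040, and 0.05/0.0040 is about 12.5 standard errors. Within one arm (2,400 against 4,800) it is about 8.9, and between arms after implementation (4,800 each) about 11.8. Every reading reproduces the claim, so it does not show which contrast was planned.

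**The literal group coefficient.** Inputs: 2,400 pre and 4,800 post prescriptions per arm (Protocol 2.1.4, equal split) and a 7.1% baseline. Active declines of 50% (Protocol 1.3) and 40% (SAP Table 2) come from the documents; passive declines are assumed. Write B for the baseline rate and r for 1 − decline. Post volume is twice pre volume in both arms, so with or without a period main effect the group coefficient is

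B_A(1 + 2r_A) / [B_P(1 + 2r_P)],

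while the difference in decline is r_A / r_P.

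| Declines, active/passive | Expected PIMs over both periods | Group coefficient, equal baselines | Ratio of post/pre rate ratios | Share of log effect kept |
|---|---|---|---|---|
| 50% / 40% | 340.8 / 374.9 | 0.909 | 0.50/0.60 = 0.833 | 52% |
| 50% / 30% | 340.8 / 409.0 | 0.833 | 0.50/0.70 = 0.714 | 54% |
| 40% / 20% | 374.9 / 443.0 | 0.846 | 0.60/0.80 = 0.750 | 58% |

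**Unequal baselines.** With identical declines the formula returns B_A/B_P. The lowest and highest percentages in SAP Table 1 give 7.61/5.9 = 1.29, an arm effect where there is none. The sign reverses once B_A/B_P exceeds the inverse of the equal-baseline coefficient: 1.10, 1.20 and 1.18 for the three rows. For example, baselines of 8.5% active and 7.5% passive with 50/40 declines give (8.5/7.5) × 0.909 = 1.03, although the ratio of rate ratios is 0.833.

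**How often that happens.** The Table 1 counts (461/7,756, 545/7,164, 1,345/18,868) have a log SD of 0.128; three sites leave a 95% interval of 0.07 to 0.80. At an assumed log SD of 0.13, the thresholds are passed in about 15%, 2.5% and 3.5% of simple 4:4 allocations. If allocation is stratified on PIM level, the shares are about 5%, 0.1% and 0.3%.

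**Scale.** Baselines of 8.0% active and 9.6% passive with declines of 40% and 35% give a ratio of 0.60/0.65 = 0.923, favouring active. The absolute reductions are 8.0 × 0.40 = 3.20 and 9.6 × 0.35 = 3.36 points, favouring passive.

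**Inference on the interaction.** Simulation: 20,000 runs, 4 against 4 sites, 600 pre and 1,200 post prescriptions per site, 40% declines in both arms. A naive Poisson interaction has type I error of about 10% if site declines vary with log SD 0.13, about 17% at 0.20, and 5% if they do not vary. A t test on site-level log change stays near 5%.

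Interval width at 50/30 and decline log SD 0.13: the site variance is 1/42.6 + 1/42.6 + 0.0169 = 0.0638 (active) and 1/42.6 + 1/59.6 + 0.0169 = 0.0571 (passive). SE = √(0.0638/4 + 0.0571/4) = 0.174, so on 6 df the 95% factor is exp(2.447 × 0.174) = 1.53. The naive SE, √(3/170.4 + 1/238.6) = 0.148, gives exp(1.96 × 0.148) = 1.34.

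**The case against.** The strongest reply is that the target is clear in words. The hypothesis speaks of decline, the endpoint of reduction from baseline, the sample-size section of change, and the regression sentence sets pre against post before it adds group. SAP section 6 is a list of covariates, not a full model. This stands: the documents do not exclude an interaction, and a reader who inferred that they do would go too far. But the model term is still missing, and a post-only comparison, a baseline-adjusted one and the 12-month between-group margin in SAP Table 2 can also be read into the text.

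A reader might also infer that the result is likely to point the wrong way. The documents do not support that. Reversal needs the active arm to start about 10–20% higher in relative terms, and for two of the three scenarios it is rare. The worked reversals are also small beside sampling error: 1.03 corresponds to 408 against 396 expected PIMs, with a naive 95% interval of 0.90 to 1.18. They show that the contrasts differ, not that a wrong conclusion is probable.

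Nor does the adjustment clause say that the primary contrast may change; it concerns methods and data properties. The narrower point is that if no contrast is named, one chosen after the data are seen would not show as a change. The negative binomial option answers site variation in decline only in part, because it allows for extra variance in counts but not for correlation of change within a site.

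**Conclusion.** The point holds as an incomplete and, if followed literally, mis-targeted statement of the primary analysis. The dilution to 52–58% of the log effect and the carry-over of baseline imbalance follow from the model form and the planned volumes; the individual ratios rest on assumed passive declines and arm baselines. The reversal shares rest on a baseline log SD estimated from three sites, and the type I error and interval figures on a between-site variation in decline that the documents do not give. These illustrate size and should not be quoted as forecasts. The conclusion does not depend on sign reversal, and it makes no claim that the change contrast gains power.

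Three related matters are secondary:

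- SAP section 3 stratifies on the share of ED prescriptions written for patients aged 65 or over, whereas SAP section 6 labels the stratum high or low PIM prescriber.
- The post period starts "following the implementation of EQUIPPED provider feedback at the local site", but at one randomised site kept in the intention-to-treat set "the site decided to pause EQUIPPED implementation until at least spring 2021". Prescribing data will still be collected there; only its index date is open.
- SAP Table 2 sizes a non-inferiority comparison that has no stated role in the analysis.

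**What to change.** In Protocol 2.1.3 and SAP sections 1 and 6, replace the group-variable sentence with one pre-specified primary contrast and its scale. The natural choice in the stated model is group by period: the ratio of post/pre rate ratios, active against passive. A post-period comparison adjusted for each site's baseline PIM rate is an acceptable alternative.

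Base inference on between-site variation in change, since Protocol 2.0 expects implementation to differ by site. Use either a random site-by-period effect with a small-sample correction or site-level log change on about 6 df (5 with stratum, and one fewer in the seven-site analysis). If fixed site effects are used, omit the group and stratum main effects, which are aliased with site.

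In the same amendment, reconcile the two stratum definitions and adjust for the one used to randomise, give the paused site an index date for the intention-to-treat analysis, and state the role of the Table 2 contrast.

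No new data or software are needed. Because sites have already been randomised, the change needs a dated and justified amendment. It also brings wider intervals: under the assumptions above, the estimate is multiplied or divided by about 1.53 with eight sites (about 1.62 with seven), against 1.34 for the naive interaction. The naive interval is too narrow if site declines vary.
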